8.2 Datasets Analysed

Four analysis populations, the modified Intent-to-Treat (mITT) population, the Per Protocol (PP) population, the Completers population, and the Safety population, will be defined as follows:

- **The mITT population** will include all randomized subjects who take at least one dose of study medication and have at least one diary entry. This dataset will be used for summarization of demographic and baseline characteristic data, and for all efficacy analyses.
- **The PP population** will consist of all mITT subjects who met all eligibility (i.e., inclusion/exclusion) criteria at study entry, did not have any major protocol violations, had an overall diary compliance of at least 70%, and had a dosing compliance within 75% to 125%. Dosing compliance will be verified by the use of diary data. Supportive efficacy analyses will be performed on this population to evaluate the impact of major protocol violations.
- **The Completers population** will consist of only those subjects who complete the entire treatment period of the study with a recorded primary endpoint and will be used for supportive efficacy analyses.

- **The Safety population** will consist of all randomized subjects who take at least one dose of double-blinded study medication. Analyses on the Safety population will be based on the actual treatment received.

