Laboratory Tests – Urine and blood samples will be collected and sent to a central laboratory for analysis (see [Section 6.3](#) for details).

Pregnancy Test – All female subjects of childbearing potential will have a serum pregnancy test performed at Screening and a urine pregnancy test at Randomization and Follow-up. Childbearing potential will be defined as any female subject who has not undergone surgical sterilization within the last 3 months or who is not post-menopausal for at least 1 year.

Adverse Events – AEs will be reported by the subject from the time of informed consent through the end of the follow-up period. AEs will be followed by the Investigator as determined by Sponsor or designee. Further details on AE reporting are provided in [Section 7](#).

Concomitant Therapy – A complete history of medications (prescribed and over-the-counter [OTC]) used within the past 30 days will be recorded, including herbal remedies and contraceptives. A full history of constipation medication use should be collected, with particular focus on any constipation medications taken within the 90 days prior to screening. The subject must be instructed to stop all disallowed prescription and laxative medications per [Section 5.7.1](#) of the protocol. A subject who has been routinely administering a daily fiber supplement and/or concomitant blood pressure lowering medication for at least 30 days preceding the Screening Visit may remain on the supplement/medication throughout the study provided the regimen and dose does not change.

Drug Accountability – All study medication received at the site will be inventoried and accounted for throughout the study and the result recorded in the Drug Accountability Form and in subject's eCRF. Study medication supplies for each subject will be inventoried and accounted for throughout the study. Study medication administration will be documented in the source documentation, including dispensation information and capsule counts, and entered in the appropriate eCRF page.

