8.4 Analysis of Exposure to Study Medication, Rescue Medication, and Concomitant Medication

8.4.1 Analysis of Study Drug Exposure and Compliance

Exposure to study medication and study drug compliance will be summarized by treatment group and overall using descriptive statistics. The exposure to study medication is defined as the last dose date of study medication minus the first dose date of study medication plus 1 day. Percent compliance will be calculated as the total number of daily dose divided by the total number of expected doses. The total number of expected doses will be calculated as the total number of study medication exposure (day) times 2.

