APPENDIX 3 SUBJECT BOWEL HABITS DIARY

The electronic diary will be completed each evening by the subject. The diary will be set up so that it may be completed each evening with responses based upon the last day.

Item/Instruction Text	Response Options
INSTRUCTIONS DAILY ASSESSMENTS The following questions will be assessed as part of the subject's daily diary. Subject will record their answers to these assessments for the entire duration of the study. Diaries are to be completed from the beginning of the screening period through the end of the double-blinded treatment period. Please note that the questions may be asked in an order different from what is presented below.	
STUDY MEDICATION Did you take your Morning Dose of STUDY MEDICATION today?	Yes No
What time did you take the Morning of STUDY MEDICATION Dose?	Morning Dose – xx:xx AM
STUDY MEDICATION Did you take your Evening Dose of STUDY MEDICATION today?	Yes No, not yet No, not taking tonight
What time did you take the Evening Dose of STUDY MEDICATION today?	Evening Dose – xx:xx PM
RESCUE MEDICATION Over the last day: Did you take a RESCUE MEDICATION to help you have a bowel movement?	Yes No
[If YES] Please indicate the OTHER RESCUE MEDICATION you used?	Bisacodyl Saline enema Other
[X will be equal to the other medicine selected in prior item response.] Did you take this RESCUE MEDICATION today or yesterday?	Today Yesterday

X	[spinner xx:xx]																					
Please record the time of this dose of RESCUE MEDICATION.																						
BOWEL MOVEMENTS Confirm you would like to report a Bowel Movement you had today or yesterday: Today's Date: DD MON YYYY Yesterday's Date: DD MON YYYY	Yes No																					
Did this bowel movement occur today or yesterday? - Will be asked for each bowel movement	Today Yesterday																					
Please record the time of this bowel movement. - Will be asked for each bowel movement	[spinner xx:xx]																					

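### The plan has no rule for doses the diary did not record, so a fully dosed subject with two blank diary days can meet the 70% diary rule yet fail the 75% dosing rule and leave the PP set

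*Combined protocol and SAP*

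**What the plan says.** Section 8.2 (Datasets Analysed) sets two numerical conditions for PP membership: the subject "had an overall diary compliance of at least 70%, and had a dosing compliance within 75% to 125" percent. It then names the source for the second: "Dosing compliance will be verified by the use of diary data". The period over which overall diary compliance is measured is not given.

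Section 8.4.1 gives the formula: "Percent compliance will be calculated as the total number of daily dose divided by the total number of expected doses". For the denominator, "The total number of expected doses will be calculated as the total number of study medication exposure (day) times 2". Exposure runs from first to last dose date inclusive, but no data source is named for those dates or for the numerator.

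Appendix 3 has one morning and one evening medication item per diary. The evening item reads "Did you take your Evening Dose of STUDY MEDICATION today". Besides yes, its answers are "No, not yet No, not taking tonight". The rescue and bowel movement items can be answered for today or yesterday; the medication items cannot.

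Other dose records exist. Section 5.5 has subjects report an omitted dose in the diary and has site staff record the time of a late dose. Section 6.1.1 (Drug Accountability) has study medication administration documented, "including dispensation information and capsule counts, and entered in the appropriate eCRF page". The PP definition uses none of these.

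Section 8.5.2 places the primary analysis in PP. Section 8.1 allows 10% for subjects outside PP or without a Week 1 count.

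**The concern.** The diary rule tolerates some blank days. The dosing rule is read from the same diary, and a blank day cannot be filled in later because the medication items cover only the current day. Each blank day therefore removes two doses from what the diary can show, whatever the subject took. The listed items also give no later chance to record an evening dose after a not-yet answer.

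The plan says nothing on either case. A programmer who divides doses found in the diary by expected doses would, without any stated decision, treat unrecorded doses as not taken. Fully dosed subjects would then leave the primary analysis set because of diary habits, drawing on a loss allowance meant for all causes.

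There is also a sign that source and rule were not matched. With at most two recordable doses a day and an expected count of two a day, diary-based compliance cannot exceed 100%, so the 125% upper limit cannot operate on diary data.

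**Working it through.** **The plan's own allowance.** From Section 8.1: 156 evaluable per group and 10% loss. 156 / 0.90 = 173.3, rounded up to 174; 3 × 174 = 522. This reproduces the plan. The allowance is 174 − 156 = 18 subjects per group, for all reasons.

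**Thresholds on the treatment week.** Seven days, two doses a day, 14 expected doses.
- Diary rule: 0.70 × 7 = 4.9, so 5 entries are needed and two blank days are allowed.
- Dosing rule: 0.75 × 14 = 10.5, so 11 recorded doses are needed (11/14 = 78.6%).

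**Fully dosed subject, unrecorded doses not credited, denominator 14.**

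| Blank days | Diary rule | Dosing rule |
|---|---|---|
| 1 | 6/7 = 85.7%, pass | 12/14 = 85.7%, pass |
| 2 | 5/7 = 71.4%, pass | 10/14 = 71.4%, fail |
| 3 | 4/7 = 57.1%, fail | 8/14 = 57.1%, fail |

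The two rules part at exactly two blank days. If the Day 1 morning dose observed in clinic is in the diary although that evening's entry is blank, the 6 of 21 two-day patterns that include Day 1 reach 11/14 and pass.

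**Not-yet answers.** With all seven diaries complete, four uncredited evening doses give 10/14, a fail. With one blank day, two are enough: 12 − 2 = 10.

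**Denominator built from diary dose dates.** If Section 8.4.1's first and last dose dates come from the diary, a blank at either end shortens exposure. Blank Days 6 and 7 give 10/10 = 100%; blank Days 3 and 4 give 10/14 = 71.4%. There are C(7,2) = 21 two-day patterns. Those with both blanks within Days 2 to 6 fail: C(5,2) = 10. The other 11 pass. True dosing is the same in all 21.

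**How many subjects.** The documents give no completion rate. Assume every dose is taken, Day 1 is complete, and Days 2 to 7 are each completed independently with probability p. The share passing the diary rule but failing the dosing rule is:
- fixed denominator of 14: C(6,2) × (1 − p)² × p⁴;
- diary-derived denominator: that value × 10/15, since 10 of the 15 patterns within Days 2 to 7 avoid Day 7.

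| p | Fixed 14 | Per 174 | Diary-derived | Per 174 |
|---|---|---|---|---|
| 0.95 | 3.1% | 5.3 | 2.0% | 3.5 |
| 0.90 | 9.8% | 17.1 | 6.6% | 11.4 |
| 0.85 | 17.6% | 30.7 | 11.7% | 20.4 |

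If 10% of completed evenings were also answered not yet and never updated (a further assumption), the fixed-14 figures become 5.9%, 14.0% and 22.3%.

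**Precision.** If these losses come on top of the planned 10%, interval width on the analysis scale grows by about 1/√(1 − loss). On the fixed denominator this is 1.6%, 5.3% and 10.2%; on the diary-derived one, 1.0%, 3.4% and 6.4%.

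**Period for diary compliance.** If it includes a 14- to 17-day screening period, there are 21 to 24 days, 15 to 17 entries are needed, and 6 to 7 may be missing. More blank treatment days then pass the diary rule, so the mismatch widens.

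**The case against.** The strongest reply is that nothing in the documents says an unrecorded dose counts as missed. Section 5.5 makes an omission something the subject reports, which differs from a blank. Appendix 3 separates a pending evening dose from one that will not be taken. Section 8.2 says compliance is verified by the diary, which need not make the diary the only record, and Section 8 leaves further detail to a SAP finalised before unblinding. All of this stands: a reader might infer that the plan scores blanks as missed doses, but the documents leave the treatment open.

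A reader might also infer that the dosing rule cancels the diary allowance. It does not. One blank day always passes, and on a diary-derived denominator so do 11 of the 21 two-day patterns. Two joint conditions, one stricter than the other, are not a contradiction.

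The device may re-prompt after a not-yet answer. Section 6.2.1 refers usage detail to a vendor manual, and Appendix 3 shows only the items. Evening doses go with meals and the diary is prompted before bedtime, so such answers may be few. Subjects have also already met a 70% diary rule in screening, so completion may be high.

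Section 8.5.1 runs efficacy analyses in both mITT and PP, and Section 8.2 calls the PP analyses supportive, at odds with Section 8.5.2. An mITT result would help show what the exclusions do.

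What remains is that the named source and formula, applied without a further rule, can exclude fully dosed subjects for gaps the diary rule permits.

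**Conclusion.** The point holds as a gap in the definition with a concrete consequence. It matters because Section 8.5.2 makes PP the primary analysis set. If unrecorded doses are not credited, tolerance falls from two blank treatment days to one on 14 expected doses. On a diary-derived denominator, membership depends on which days are blank.

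The size is conditional on the assumed completion rates and independence between days: roughly 3% to 18% of fully dosed subjects on the fixed denominator and 2% to 12% on the other, for completion of 95% down to 85%. At 90%, the effect alone takes from about two-thirds (6.6%) to nearly all (9.8%) of the 10% allowance; at 95% it is small.

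A reader might go on to infer a biased sprinkle-to-capsule ratio. The documents do not support that: all arms follow the same double-dummy regimen and use the same diary, and nothing suggests different completion by arm. The demonstrated effect is fewer PP subjects and lower precision. This is a cheap improvement to make before the SAP is finalised.

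**What to change.** In Sections 8.2 and 8.4.1:
- keep the diary as the source for days with an entry;
- class doses on days without an entry, or with only a not-yet answer, as not recorded, and resolve them from the capsule counts and site dose records already collected;
- take the last dose date from all dose records;
- state the period over which overall diary compliance is measured.

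In Appendix 3, after a not-yet answer, add a next-day item asking whether yesterday's evening dose was taken and when. This matches the today-or-yesterday choice already given for bowel movements and rescue.

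Replacing the diary outright with returned-unit counts is a more debatable step and is not needed.

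Cost: a few sentences and one conditional diary item. Capsule counts can be distorted by late, unreturned or discarded units and do not show when a dose was taken, so they should settle only unrecorded doses.

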8.3 Analysis of Subject Characteristics and Completion Status

Subject demographic and baseline disease characteristic data will be summarized by treatment group and overall with descriptive statistics for all randomized subjects. The summaries will include the number of subjects, mean, median, standard deviation, minimum, maximum, 95% confidence intervals (CIs) for continuous variables, and counts and percentages for each level of categorical variables. Treatment comparisons will be presented using two-sample t-test for continuous variables and Cochran-Mantel-Haenzel (CMH) test for categorical variables.

For Subject completion status, the frequencies and percentages of subjects who are randomized, treated, completed study, discontinued from study with reasons for discontinuation will be summarized by treatment group and overall. Subject accountability will be summarized by site and by treatment group and overall for randomized subjects and all study specific populations.

8.4 Analysis of Exposure to Study Medication, Rescue Medication, and Concomitant Medication

8.4.1 Analysis of Study Drug Exposure and Compliance

Exposure to study medication and study drug compliance will be summarized by treatment group and overall using descriptive statistics. The exposure to study medication is defined as the last dose date of study medication minus the first dose date of study medication plus 1 day. Percent compliance will be calculated as the total number of daily dose divided by the total number of expected doses. The total number of expected doses will be calculated as the total number of study medication exposure (day) times 2.

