8.1 Determination of Sample Size

This is a phase 3, multicentre, double-blinded, randomized, placebo-controlled study evaluating the bioequivalence of Sprinkle and Capsule formulations of lubiprostone when administered orally in subjects with chronic idiopathic constipation. Subjects will be randomized (1:1:1 ratio) to receive either lubiprostone sprinkle, lubiprostone capsule or matching placebo BID in a blinded, double-dummy fashion.

In clinical studies of the lubiprostone capsule formulation during the CIC development program, the average observed SBM count at Week 1 for lubiprostone 24 mcg BID was 5.62 with a standard deviation of 4.24. In order to achieve the conclusion of equivalence between the sprinkle and capsule formulations of lubiprostone, the 90% confidence interval for the ratio of means has to be contained within the interval of [0.8, 1.25]. Thus, a sample size of 156 per group is required to achieve 90% power at a 10% significance level.

Assuming 10% of subjects do not meet criteria for inclusion in the Per Protocol population and/or do not have observed week 1 SBM count due to early withdrawal or other reasons, 174 subjects per treatment group (a total of 522 subjects) will be required for this study.

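### The only dosing-compliance formula stops counting at the subject's own last dose, so the 75% floor for the per-protocol population does not detect early stopping

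*Combined protocol and SAP*

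**What the plan says.** Section 8.4.1 defines exposure as the "last dose date of study medication minus the first dose date of study medication plus 1 day". It then states: "Percent compliance will be calculated as the total number of daily dose divided by the total number of expected doses". The denominator follows: "The total number of expected doses will be calculated as the total number of study medication exposure (day) times 2". This is the only compliance formula in the document.

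Section 8.2 admits to PP those mITT subjects who were eligible, had no major protocol violation, and "had an overall diary compliance of at least 70%, and had a dosing compliance within 75% to 125" per cent. On the source of the dosing figure it says only: "Dosing compliance will be verified by the use of diary data". It does not cite 8.4.1, and it defines neither the diary denominator nor a major violation. Completing treatment is a condition of the separate Completers population, not of PP.

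Section 8.5.2 runs the primary equivalence analysis in PP. Section 8.2 describes PP analyses as supportive; I follow 8.5.2 on which population is primary. Section 8.5.4 describes a sensitivity analysis that keeps some PP subjects who discontinued early and removes others.

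**The concern.** A PP analysis supports an equivalence claim when it compares subjects who were adequately dosed. A compliance floor that resets to each subject's own stopping date does not secure that. It picks up doses skipped before the last dose but not the doses never taken afterwards.

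Two things are at stake. If a subject stops drug but keeps the diary, the Week 1 count includes days off drug. Where this happens in both active arms, those days tend to look alike and pull the ratio of means toward 1, which favours a finding of equivalence. If the diary stops as well, the last-daily-observation rule in 8.5.1.1 fills the rest of the week from the last recorded day, and that can move the count either way. In neither case is the weekly count a measure of a week on treatment.

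**Working it through.** **Inputs.** Two doses a day (Section 5.5) for 7 days (Section 5.5.1) gives 2 × 7 = 14 planned doses. The PP floor is 75% (Section 8.2). The formula is in Section 8.4.1. The plan gives no compliance figure for an early stopper, so there is none to reproduce.

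**Assumption.** Doses are consecutive from the morning of Day 1. After k doses the last dosing day is then k/2, rounded up.

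**Formulas.** By 8.4.1: k ÷ (2 × last dosing day). Against the plan: k ÷ 14.

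| Doses taken, then stopped | Last dosing day | By 8.4.1 | Meets 75% floor? | Against 14 | Meets 75% floor? |
|---|---|---|---|---|---|
| 1 | 1 | 1/2 = 50.0% | no | 7.1% | no |
| 2 | 1 | 2/2 = 100% | yes | 14.3% | no |
| 3 | 2 | 3/4 = 75.0% | yes | 21.4% | no |
| 4 | 2 | 4/4 = 100% | yes | 28.6% | no |
| 5 | 3 | 5/6 = 83.3% | yes | 35.7% | no |
| 6 | 3 | 6/6 = 100% | yes | 42.9% | no |
| 7 | 4 | 7/8 = 87.5% | yes | 50.0% | no |
| 8 | 4 | 8/8 = 100% | yes | 57.1% | no |
| 9 | 5 | 9/10 = 90.0% | yes | 64.3% | no |
| 10 | 5 | 10/10 = 100% | yes | 71.4% | no |
| 11 | 6 | 11/12 = 91.7% | yes | 78.6% | yes |
| 12 | 6 | 12/12 = 100% | yes | 85.7% | yes |

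The two denominators disagree for every subject who stops after 2 to 10 doses. Of the early stoppers, only the one-dose subject fails under 8.4.1.

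**Order reversed.** Ten doses spread from Day 1 to Day 7 give 7 exposure days, 14 expected doses and 10/14 = 71.4%, so the subject is excluded. Two doses on Day 1 and none after give 100%, so the less exposed subject passes.

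**Does the 70% diary criterion close the gap?** Take a subject who stops drug after Day 2.

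- Diary kept to Day 7: 7/7 on treatment days. With 14 screening days included, 21/21 if screening was complete and (10 + 7)/21 = 81.0% with 10 of 14 screening entries. Passes in each case.
- Diary also stops after Day 2: 2/2 on the subject's own days, or (14 + 2)/21 = 76.2% with complete screening. Passes.
- Diary also stops after Day 2, other counts: 2/7 = 28.6% on treatment days, or (10 + 2)/21 = 57.1% with 10 of 14 screening entries. Fails.

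The answer depends on a diary denominator that 8.2 does not state.

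**The case against.** The strongest objection is that the link is inferred. Section 8.4.1 describes a summary table, 8.2 does not refer to it, and the opening of Section 8 leaves detail to a SAP that may state another denominator. That stands as a limit on certainty. But 8.4.1 is the only formula given, and a reader applying 8.2 has nothing else to use.

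It can also be said that adherence while on drug is a legitimate measure, and that persistence is a different one. That is fair for a descriptive table. It does not explain why the criterion for the primary population should keep a two-dose subject and exclude a ten-dose subject.

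The plan has other safeguards: mITT as well as PP analyses (8.5.1), the Completers population (8.2), the 8.5.4 analysis and alternative imputations (8.5.1.1). They make the effect visible, but they do not change who is in the primary analysis.

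A reader might infer more than the text supports:

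- *Every early stopper scores about 100% and enters PP.* One dose gives 50% and three give 75%. Entry also depends on the diary and major-violation criteria. The supportable statement is that the dosing criterion does not keep out those who stop after 2 to 10 doses.
- *Section 8.1 is contradicted, because its 10% allowance includes subjects who* "do not have observed week 1 SBM count due to early withdrawal or other reasons". That clause concerns a missing outcome, not dosing compliance. There is a tension, since carried-forward data can supply a count, but no contradiction.
- *Stopping drug is the main form of non-compliance, or the ratio shifts by a known amount.* The document gives no early-stopping rate. A shift built from high Day 1 counts carried forward in one arm would measure the imputation rule, not this formula.

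**Conclusion.** The point holds as a defect in a stated rule. Under the only formula given, the 75% floor passes every consecutive-dosing subject who stops after 2 to 10 of 14 doses, a true dose fraction of 14% to 71%. It excludes a subject with 10 doses spread over the week. Section 8.5.4 confirms that the plan expects some early discontinuers within PP.

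The conclusion rests on reading the 8.2 criterion with the 8.4.1 formula and on consecutive dosing from the morning of Day 1. How many such subjects reach PP depends on undefined terms and on an unstated rate of early stopping, so neither the size nor the net direction of the effect on the ratio can be given. The rule should be corrected before unblinding.

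**What to change.** - **Section 8.2:** define PP dosing compliance as doses taken divided by the 14 planned doses for every subject. The 75% floor then needs at least 11 doses, since 10/14 = 71.4% fails and 11/14 = 78.6% passes.
- **Section 8.4.1:** keep the exposure-based ratio for the descriptive table only, and say that it does not determine PP membership.
- **Section 8.5.4:** change it at the same time. It retains lack-of-efficacy discontinuers who completed 3 days. With a 14-dose denominator, stopping after Day 3, 4 or 5 gives 6/14 = 43%, 8/14 = 57% or 10/14 = 71%, so nearly all of that group would drop out of PP. Draw its lack-of-efficacy and rescue discontinuers from mITT subjects who meet the other PP criteria.

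The cost is a short text change in three sections. The statistical downside is that a few subjects leave PP because of events after randomization, some of them for efficacy or tolerability reasons. If these differ between formulations, their removal could hide a difference. The mITT analysis already planned in 8.5.1 shows the effect of removing them. Section 8.1 allows 10% for subjects lost from PP or without a Week 1 count, which is 174 − 156 = 18 per arm. Early stoppers would share that allowance with all other losses.
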